5.2. Treatment Arms and Duration

Two treatment arms will be employed for the study:

- FF/VI 100/25 mcg QD via ELLIPTA + Placebo BD via Diskus
- FP 250 mcg BD via Diskus + Placebo QD via ELLIPTA

As this is a 2-period cross-over study, all randomized subjects will receive both treatments in the study either in Treatment Period 1 or Treatment Period 2. Also, each subject will receive a Diskus and ELLIPTA inhaler in Treatment Period 1 and Treatment Period 2.

Subjects will complete a 4-week single blind run-in on FP 250 mcg twice daily, followed by 2-week double-blind Treatment Period 1 on randomized treatment, a 2-week single blind washout period on FP 250 mcg twice daily, 2-week double-blind Treatment Period 2 receiving the alternative treatment, and follow-up contact approximately 7-days after completing Treatment Period 2. The total duration of study participation is approximately

11 weeks; and up to 15 weeks for subjects with SAR at screening who may need to be treated with intranasal corticosteroids followed by repeat screening visit.

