8.3.3.4. Visit 4 and Visit 7 (Blinded Treatment Exercise Challenges)

Visit 4 and Visit 7 begin between 5 PM and 11 PM and are conducted over approximately 24 hours. Subjects will be required to attend three clinic visits during each 24-hour period for Visit 4 and Visit 7. The evening visit should begin at approximately the same time as Visit 1 (± 1 hour).

Dosing: At the beginning of Visit 4 and Visit 7, subjects will administer their evening doses of double-blinded study medication in the clinic and the time of dosing will be recorded. In addition to administering the evening dose, vital signs will be measured and a review of concomitant medication and AEs performed.

Subjects will return to the clinic 12 (± 1) hours and 23 (± 1) hours after evening dosing for exercise challenge testing.

Pre-exercise FEV₁: At least two valid spirometry efforts with full FEV₁ and FVC maneuvers should be obtained just prior to each exercise challenge.

From this spirometry testing, the target FEV₁ values #2 and #3 (Section 8.3.1.1) should be determined based on the pre-exercise FEV₁.

Exercise challenge testing: Exercise challenge testing will occur at 12 (± 1) hours and 23 (± 1) hours after administering the evening dose. (The 12-hour exercise challenge and spirometry measurements should occur prior to dosing of the study medication).

Post-exercise Serial Spirometry: Following the eligibility exercise challenge at each visit, serial spirometry (FEV₁) will be performed at 5, 10, 15, 30, 45 and 60 minutes post-exercise.

Washout Medication Dosing: At the end of Visit 4, the washout medication should be dispensed and first evening dose administered following completion of the 23-hour post evening dose exercise challenge/serial spirometry, and prior to the subject's leaving the clinic.

8.3.3.5. Visit 5

Treatment period 2 baseline FEV₁: Spirometry will be performed at Visit 5 at approximately the same time as at Visit 1 (± 1 hour). The FEV₁ should be measured approximately 12 hours (± 1 hour) after dosing with the washout medication. At least two valid spirometry efforts should be obtained.

Dosing: Subjects will administer their evening doses of double-blinded study medication following the spirometry.

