8.2.1.1. Adverse Events of Special Interest

The number and percentage of subjects with adverse events of special interest to FF and/or VI will be summarized for each treatment by special interest term, subgroup and preferred term (PT). The ordering of the special interest terms, the subgroups and the PTs within them will all be in descending order of total incidence. If the total incidence for any two or more adverse events is equal, the events will be presented in alphabetical order. This summary will include both on-treatment and post-treatment AEs.

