10.4.1.2. Treatment States for Adverse Events and Severe Asthma Exacerbations

Treatment states for adverse events are described below. Severe asthma exacerbations will be treated in the same way, with the exacerbation start date used in place of the AE start date.

Treatment State	Definition
Pre-Treatment	AE start date \leq first dose date of the study -1
On-Treatment	First dose date of treatment period \leq AE start date \leq last dose date of treatment period + 1
Post-Treatment	AE start date \geq last dose date of study + 2 OR Last dose date of treatment period + 2 \leq AE start date \leq first dose date of next treatment period - 1

AEs occurring during the washout period or during the follow-up period are therefore classified as post-treatment and will be summarized under the treatment from the previous period.

Note: Time Since 1st Dose will be derived as follows:

- If the First Dose Date or the AE Onset Date are missing then => missing
- If First Dose Date > AE Onset Date then => AE Onset Date – First Dose Date
- If First Dose Date \leq AE Onset Date then => AE Onset Date - First Dose Date +1

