10.13.5. Safety Tables

Safety : Tables			
No.	Population	IDSL Basis	Title
Adverse Events Including Pneumonia			
3.1.	ITT	-	Adverse Event Overview
3.2.	ITT	AE1	Summary of On-Treatment Adverse Events - Intent-to-Treat
3.3.	ITT (15 Years or Older)	AE1	Summary of On-Treatment Adverse Events - ITT (15 Years or Older)
3.4.	ITT (12-17 Years Old)	AE1	Summary of On-Treatment Adverse Events - ITT (12-17 Years Old)
3.5.	ITT	AE1	Summary of Post-Treatment Adverse Events
3.6.	ITT	AE3	Summary of Most Frequent On-Treatment Adverse Events
3.7.	ITT	-	Summary of the Most Frequent On-treatment Adverse Events - Top Ten Most Commonly Reported On-treatment Adverse Events Per Treatment Group
3.8.	ITT	AE1	Summary of Drug-Related Adverse Events
3.9.	ITT	AE1	Summary of Drug-Related Serious Adverse Events
3.10.	ITT	AE1	Summary of Adverse Events Leading to Permanent Discontinuation of Study Drug or Withdrawal From the Study
3.11.	ITT	AE1	Summary of On-Treatment Serious Adverse Events
3.12.	ITT	AE1	Summary of Post-Treatment Serious Adverse Events
3.13.	ITT	-	Summary of Common On-Treatment Non-Serious Adverse Events (>=3% without rounding)
3.14.	ITT	-	Summary of On-Treatment Serious Adverse Events
3.15.	ITT	-	Summary of On-Treatment Fatal Adverse Events
3.16.	ITT	-	Summary of Post-Treatment Fatal Adverse Events
3.17.	ITT	-	Summary of On-Treatment and Post-Treatment Adverse Events of Special Interest - Intent-to-Treat
3.18.	ITT (12-17 Years Old)	-	Summary of On-Treatment and Post-Treatment Adverse Events of Special Interest - ITT (12-17 Years Old)
3.19.	ITT	-	Summary of On-Treatment and Post-Treatment Serious Adverse Events of Special Interest - Intent-to-Treat
3.20.	ITT	-	Summary of On-Treatment Pneumonia
3.21.	ITT	-	Summary of Post-Treatment Pneumonia
3.22.	ITT	AE2	Relationship of Adverse Event System Organ Class, Preferred Term and Verbatim Text
3.23.	ITT	-	Record of all Preferred Terms That Could Have Mapped to Special Interest Terms

Safety : Tables			
No.	Population	IDSL Basis	Title
Severe Asthma Exacerbations			
3.24.	ITT	-	Summary of Subjects with Severe Asthma Exacerbations - Intent-to-Treat
3.25.	ITT (15 Years or Older)	-	Summary of Subjects with Severe Asthma Exacerbations - ITT (15 Years or Older)
3.26.	ITT (12-17 Years Old)	-	Summary of Subjects with Severe Asthma Exacerbations - ITT (12-17 Years Old)
Other			
3.27.	ITT	VS1	Summary of Vital Signs
3.28.	ITT	VS1	Summary of Change from Baseline in Vital Signs

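### Special-interest adverse events that start on washout FP after FF/VI are counted under FF/VI in Tables 3.17–3.19, which shrinks the relative difference between treatments

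*SAP*

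**What the plan says.** Protocol section 5.2 places "a 2-week single blind washout period on FP 250 mcg twice daily" between the two treatment periods, for both sequences. At Visit 4 (Protocol section 8.3.3.4) "the washout medication should be dispensed and first evening dose administered following completion of the 23-hour post evening dose exercise challenge/serial spirometry", so FP starts the same evening.

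SAP section 10.4.1.2 ends the on-treatment window at "last dose date of treatment period + 1". Later events, up to the day before the next period's first dose, are post-treatment: "AEs occurring during the washout period or during the follow-up period are therefore classified as post-treatment", and they "will be summarized under the treatment from the previous period".

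For special-interest events, SAP section 8.2.1.1 states: "The number and percentage of subjects with adverse events of special interest to FF and/or VI will be summarized for each treatment". It adds: "This summary will include both on-treatment and post-treatment AEs". The list of safety tables (SAP section 10.13.5) carries this scope into the titles. Table 3.17 is the "Summary of On-Treatment and Post-Treatment Adverse Events of Special Interest - Intent-to-Treat", Table 3.18 repeats it for ages 12–17, and Table 3.19 covers serious special-interest events. No on-treatment-only special-interest table is listed.

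Other displays are split. On- and post-treatment events have separate tables for all adverse events (3.2 and 3.5), serious events (3.11 and 3.12), fatal events (3.15 and 3.16) and pneumonia (3.20 and 3.21). Protocol section 10.4.2.2 plans tabulation by treatment group of events occurring in the treatment period. SAP section 10.4.1.1 gives concomitant medications a washout state of their own; adverse events have none.

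**The concern.** The washout is not drug-free: it is the comparator at the comparator's dose and frequency. For a subject in the FF/VI-then-FP sequence, an event that starts about two weeks after the last FF/VI dose, on FP, is counted as an FF/VI event. For the other sequence the same rule adds FP time to the FP column, so attribution is disturbed on one side only.

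These tables group the known ICS and LABA risks. If FF/VI carries a higher risk of such events, mixing FP-only time into its percentage makes the two columns look proportionally more alike, and the grouped display has no undiluted counterpart.

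**Working it through.** The plan states no special-interest event rate and no power for these tables, so there is no planned figure to reproduce. The check sets out the counted days and then shows what pooling does to an assumed true difference.

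**Inputs from the documents**
- Two sequences, 1:1 (Protocol section 7.2). With no withdrawals, half of each column's subject-periods are followed by washout and half by follow-up.
- Visit 2 on day 0, Visit 4 on day 14, Visit 5 on day 28, Visit 7 on day 42, follow-up contact on days 47–51, with day 49 used here (Protocol Table 3).
- Windows from SAP section 10.4.1.2: on-treatment to last dose + 1 day; post-treatment from last dose + 2 days.
- The last dose falls on period day 15 if a morning Diskus dose follows the 12-hour challenge (Protocol section 8.3.3.4), otherwise on day 14. Both are shown.

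**Counted days, last dose on period day L**
- On-treatment: L + 2. Washout: 26 − L. Follow-up: 20 − L.
- L = 15: 17, 11 and 5 days. L = 14: 16, 12 and 6 days.
- Mean post-treatment days per subject-period: (11 + 5)/2 = 8, or (12 + 6)/2 = 9.
- Share of FF/VI-column time that is washout FP: 5.5/25 = 22%, or 6/25 = 24%. Among period 1 subjects alone: 11/28 = 39%, or 12/28 = 43%.

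**Assumptions**
Constant hazard, no carry-over, no withdrawals, and washout and follow-up time at the FP rate.

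**Rate ratio**
Observed ratio = (R × on + post)/(on + post), where R is the true rate ratio.

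| True R | 17/11/5 days | 16/12/6 days |
|---|---|---|
| 1.5 | (25.5 + 8)/25 = 1.34 | (24 + 9)/25 = 1.32 |
| 2.0 | (34 + 8)/25 = 1.68 | (32 + 9)/25 = 1.64 |
| 3.0 | (51 + 8)/25 = 2.36 | (48 + 9)/25 = 2.28 |

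With washout pooled but not follow-up, R = 2 gives (34 + 5.5)/22.5 = 1.76, or (32 + 6)/22 = 1.73.

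**Absolute difference**
Let λ be the FP rate per day. On the 17/11/5 schedule, expected events per subject-period are 34λ + 8λ = 42λ for FF/VI and 17λ + 8λ = 25λ for FP. The gap is 17λ, exactly the on-treatment gap of 34λ − 17λ. Pooling adds the same expected number of events to each column.

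**Proportions of subjects, the metric these tables use**
16/12/6 days, true hazard ratio 2; the FP on-treatment risk is assumed:

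| FP risk | On-treatment ratio | Pooled ratio | On-treatment difference | Pooled difference |
|---|---|---|---|---|
| 2% | 1.98 | 1.62 | 1.96 points | 1.94 points |
| 5% | 1.95 | 1.60 | 4.75 points | 4.62 points |
| 10% | 1.90 | 1.56 | 9.00 points | 8.48 points |

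At 5% the percentages move from 9.8% against 5.0% to 12.3% against 7.7%. A crude z for the difference, treating the columns as independent with 66 subjects each, falls from 1.05 to 0.89. The SAP plans no such test; the figure only shows the added noise.

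**The case against.** The best defence is that the rule is balanced. Sequences are 1:1 and both take the same washout drug for the same time, so each column gains the same expected number of events. This stands for the absolute difference. A reader might infer that pooling dilutes any FF/VI versus FP difference; the arithmetic does not support that. It does not answer the loss on the relative scale, or the counting of FP-onset events under FF/VI.

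Second, a reader might infer that a safety signal could be hidden. The other displays do not support that. Table 3.2 gives on-treatment events by treatment and preferred term, repeated by age in 3.3 and 3.4. Serious, fatal and pneumonia events are split. Listings 10–12 separate pre-, on- and post-treatment events, and Table 3.23 records the terms that could map to special-interest groups. Only the grouped subject count lacks an on-treatment version. These on-treatment displays are free of washout events except for the one-day extension after the last dose.

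Third, attribution to the previous treatment has a rationale: an event starting in washout may be a late effect of FF/VI. This stands. Relabelling every event by the drug being taken would charge late FF/VI events to FP. It would also fail for follow-up, because asthma medication started on or after the final clinic visit is not recorded (Protocol section 7.9).

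Finally, the mock shells are separate documents (SAP section 10.14), so split rows inside Tables 3.17–3.19 cannot be excluded. The SAP text does not require them.

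**Conclusion.** The point holds as a minor matter of presentation and attribution. Special-interest events that start on washout FP after FF/VI are counted in the FF/VI percentages of Tables 3.17–3.19, with no on-treatment counterpart. Under the stated assumptions a true rate ratio of 2.0 shows as about 1.64 to 1.68, while the absolute difference barely moves. The size depends on assumed rates and on there being no carry-over; to the extent that FF/VI effects persist into washout, the rule keeps those events where they belong and the dilution is smaller. The tables are descriptive, and no planned test, the primary analysis or the power is affected. The effect is to weaken a grouped signal.

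**What to change.** Specify Tables 3.17–3.19 with on-treatment events as the main treatment comparison. Show post-treatment events separately in two groups: *washout (on FP), by preceding treatment* and *follow-up, after study treatment, by preceding treatment*. Late-onset FF/VI events then stay visible without entering the on-treatment percentages. Amend SAP section 8.2.1.1 and the table titles to match.

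The cost is a table-specification change before unblinding and slightly longer tables. The pre-, on- and post-treatment states already exist. Separating washout from follow-up needs one date-based flag, and SAP section 10.6.1 already derives washout start and end dates.

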10.5. Appendix 5: Data Display Standards & Handling Conventions

10.5.1. Study Treatment & Sub-group Display Descriptors

Treatment Group Descriptions			
RandAll NG		Data Displays for Reporting	
Code	Description	Description	Order [1]
A	FF/VI 100/25mcg OD	FF/VI 100/25 OD	1
B	FP 250mcg BD	FP 250 BD	2

NOTES:

1. Order represents treatments being presented in TFL, as appropriate.

If a subject attends at least one scheduled clinic visit for a treatment period, then they will be counted as having taken part in that treatment period and will contribute to the population numbers (i.e. “Big N” numbers) for the treatment that they were randomized to receive in that period.

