6.4.1. Study Specific Withdrawal Criteria

A Subject will be withdrawn from the study if any of the following withdrawal criteria are met:

1. **Liver Chemistry:** Meets any of the protocol-defined liver chemistry stopping criteria (see [Appendix 2](#)).

Liver chemistry stopping and increased monitoring criteria have been designed to assure subject safety and evaluate liver event etiology (in alignment with the FDA premarketing clinical liver safety guidance).
<http://www.fda.gov/downloads/Drugs/GuidanceComplianceRegulatoryInformation/Guidances/UCM174090.pdf>

If the liver chemistry stopping criteria are met by any subject participating in this study, treatment restart or rechallenge is not permitted.

2. Severe Asthma Exacerbation

Subjects who experience a severe asthma exacerbation at any time during the study must be withdrawn from the study. A severe exacerbation is defined as deterioration of asthma requiring the use of systemic corticosteroids (tablets, suspension, or injection) for at least 3 days or an in-patient hospitalization or Emergency Department visit due to asthma that required systemic corticosteroids during the study.

3. Worsening of Asthma requiring additional treatment

Subjects requiring rescue therapy with anything other than MDI or nebulized albuterol/salbutamol or ipratropium (secondarily) following the exercise challenge assessment should be withdrawn.

NOTE: If a subject's FEV₁ decreases to $\geq 40\%$ from their pre-exercise FEV₁ following exercise challenge, he/she must receive rescue therapy. If he/she requires rescue therapy with anything other than MDI or nebulized

albuterol/salbutamol or ipratropium (secondarily) following the exercise challenge assessment, he/she is not allowed to continue in the study

Subjects who experience asthma worsening outside of the exercise challenges which, in the opinion of the investigator, requires additional asthma treatment other than study medication or study supplied albuterol/salbutamol should be withdrawn.

4. **Pregnancy:** Positive urine pregnancy test
5. **ECG:** Discontinuation is required if any of the following ECG criteria are met during the study:
 - QTcF>500 msec or uncorrected QT>600 msec
 - Change from baseline: QTcF> 60msec

For patients with underlying **bundle branch block**, follow the discontinuation criteria listed below:

Baseline QTc with Bundle Branch Block	Discontinuation QTc with Bundle Branch Block
< 450 msec	> 500 msec
450 – 480 msec	≥ 530 msec

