6.4.4. Early Withdrawal Visit

Subjects may withdraw or be withdrawn from the study for any reason. If withdrawal occurs, the investigator must make every effort to have the subject return to the clinic as soon as possible after the subject stopped study medication for an Early Withdrawal (EW) Visit (ideally within 24 hours). At withdrawal, all study medications and other

study-related materials should be returned to the site by the subject (Time and Events Table [Table 3](#)). In the event a subject withdraws at, or during, a scheduled visit, an Early Withdrawal Visit is not required. However, all study procedures scheduled at an Early Withdrawal Visit must be performed at this visit instead. A follow-up phone contact should be made 7 days (\pm 2 days) after the Early Withdrawal Visit.

Following completion of these procedures, the subject will be discharged from the study. Upon completion of the Early Withdrawal Visit, each subject may resume any asthma medications deemed appropriate by the investigator for the management of the subject.

In the event that a subject is withdrawn from the study due to an adverse event, the investigator must attempt to follow the subject until the adverse event has either resolved or has become clinically insignificant.

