4. ANALYSIS POPULATIONS

Population	Definition / Criteria	Analyses Evaluated
Total	
 This population will comprise all subjects screened and for whom a record exists on the study database 	
 The tabulations of reasons for withdrawal before randomization.
Intent-To-Treat (ITT)	
 This population will comprise all subjects randomized to treatment and who received at least one dose of study medication. Randomized subjects will be assumed to have received study medication unless definitive evidence to the contrary exists. Outcomes will be reported according to the randomized treatment allocation. 	
 Study population, efficacy and safety displays This will constitute the primary population for all analyses of efficacy measures and safety measures.
Per-Protocol (PP)	
 The PP Population will consist of all subjects in the ITT Population who do not have any full protocol deviations and have at least one treatment period without a partial deviation. Protocol deviations can be either full or partial. Subjects with only partial deviations in 1 treatment period will be considered part of the PP population but their data from the treatment period affected by the deviations will be excluded. Protocol deviations that would exclude subjects or part of their data from the PP population are defined in Appendix 1 (Definitions for Per-Protocol Population). 	
 This population will be used for confirmatory analysis of the primary efficacy endpoint only.
ITT (12-17 Years Old)	
 This will be a subset of the ITT population for subjects aged 12-17 years old. 	
 This population will be used for adolescent displays.
ITT (15 Years or Older)	
 This will be a subset of the ITT population for subjects aged 15 years or older. 	
 This population will be used for displays on the subset of subjects aged 15 years or older.

NOTES :

- Please refer to [Appendix 13: List of Data Displays](#), which details the population to be used for each display being generated.

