8. SAFETY ANALYSES

8.1. Safety Analyses

8.1.1. Overview of Planned Safety Analyses

The safety analyses will be based on the ITT population, unless otherwise specified.

[Table 5](#) provides an overview of the planned analyses, with further details of data displays being presented in [Appendix 13: List of Data Displays](#).

Table 5 Overview of Planned Safety Analyses

Display Type	Data Displays Generated		
	Table	Figure	Listing
Adverse Events			
Overview	Y		
AEs for Subjects not in ITT			Y ^[2]
Pre-Treatment AEs			Y
On-Treatment AEs	Y ^[3]		Y
Post-Treatment AEs	Y		Y
Most Frequent On-Treatment AEs (≥3% after rounding)	Y		
Top Ten Most Common On-Treatment AEs	Y		
Drug-Related AEs	Y		
Drug-Related SAEs	Y		
AEs Leading to Withdrawal	Y		Y
On-Treatment SAEs	Y		Y
Post-Treatment SAEs	Y		Y
Common On-Treatment Non-Serious AEs (≥3% without rounding including event numbers and drug-related event numbers)	Y		
On-Treatment SAEs (including event numbers and drug-related event numbers)	Y		
On-Treatment Fatal AEs (including event numbers and drug-related event numbers)	Y		
Post-Treatment Fatal SAEs (including event numbers and drug-related event numbers)	Y		
AEs of Special Interest	Y ^[1]		
SAEs of Special Interest	Y		
Relationship of AE System Organ Class, Preferred Term and Verbatim Text	Y		
Record of all Preferred Term's That Could Have Mapped to Special Interest Terms	Y		
Pneumonia			
On-Treatment Pneumonia	Y		Y
Post-Treatment Pneumonia	Y		Y
Chest X-ray			Y
Severe Asthma Exacerbations			
Severe Asthma Exacerbations	Y ^[3]		Y

Display Type	Data Displays Generated		
	Table	Figure	Listing
Other			
Vital Signs	Y		Y
Change from Baseline in Vital Signs	Y		
Family History of CV Risk Factors	Y		Y
IP Inhaler Malfunctions			Y

NOTES :

- Y = Yes display generated.
- [1]: Display will be based on the ITT population and repeated for the ITT (12-17 Years Old) population
- [2]: Display will be based on the inverse of the ITT population i.e. all subjects not in the ITT population
- [3]: Display will be based on the ITT population and repeated for the ITT (12-17 Years Old) population and also for the ITT (15 Years or Older) population

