10.5.2. Baseline Definition & Derivations

10.5.2.1. Baseline Definitions

In general, the subject level baseline (or study baseline) is defined as the value taken at visit 2 (randomization), and the period level baseline is defined as the pre-treatment value taken at the start of each treatment period (visit 2 and visit 5). Using these definitions the period baseline for treatment period 1 is the same as the subject level baseline.

For FEV₁ and Vital Signs, the baseline value at visit 2 will be taken from the “Pre Challenge” planned time.

The primary analysis will include as a covariate, the period baseline value as well as including as a covariate, the mean of the two period baseline values.

For the physical activity measures assessed by the biosensor, the period baseline will be derived using all the available data from the last 7 calendar days prior to, but not including the first clinic visit of the treatment period (Visit 2/5). For example, if the randomisation visit (Visit 2) was on the 18th May then the period baseline for treatment period 1 would be derived as the average of the non-missing data that is available from the 11th May to the 17th May inclusive.

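### Safety denominators set by visit attendance can include a subject withdrawn at Visit 5 who never took the Period 2 treatment

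*SAP*

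**What the plan says.** - **Counting rule.** SAP 10.5.1: "If a subject attends at least one scheduled clinic visit for a treatment period, then they will be counted as having taken part" in that period. The same sentence then adds the subject to the population "numbers) for the treatment that they were randomized to receive in that period". It sets no dosing condition.
- **Visit 5 belongs to Period 2.** SAP 10.5.2.1, on baselines, refers to "the first clinic visit of the treatment period (Visit 2/5". SAP 10.6.1 takes the date of a period's first clinic visit as its start date.
- **Dosing comes late in Visit 5.** Protocol 8.3.3.5: "Subjects will administer their evening doses of double-blinded study medication following the spirometry".
- **A subject can leave at that visit.** Protocol 6.4.4: "In the event a subject withdraws at, or during, a scheduled visit, an Early Withdrawal Visit is not required". The withdrawal criteria in Protocol 6.4.1 include "Positive urine pregnancy test", and Protocol Table 3 schedules that test at Visit 5, along with diary and adverse event review.
- **Population for safety.** SAP 8.1.1: "The safety analyses will be based on the ITT population, unless otherwise specified". SAP 4 defines ITT: "This population will comprise all subjects randomized to treatment and who received at least one dose of study medication".
- **Event attribution.** Under SAP 10.4.1.2, an event counts as on-treatment from the first dose date of the treatment period. Events in washout or follow-up are reported under the treatment of the preceding period.

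**The concern.** The numerator and the denominator rest on different bases. Events are assigned to a treatment by dose dates, but subjects are assigned to its N by attendance. A subject who comes to Visit 5 and is withdrawn there before dosing counts in the denominator of the Period 2 treatment without having been exposed to it.

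At stake are the adverse event and severe exacerbation percentages by treatment, which would be slightly too low. The N heading those tables would also exceed the number of subjects with exposure to that treatment.

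**Working it through.** **1. The plan's own figures.** Recruitment: 275 × 0.80 = 220 enter run-in; 220 × 0.30 = 66 randomised; 66 × 0.85 = 56.1, so 56 evaluable. Power for the 2×2 crossover: SE = 8 × √(2/56) = 1.512, and 5/1.512 = 3.31. The noncentral t with 54 degrees of freedom gives 0.9011, against 90.1% in Protocol Table 5. Both reproduce. For this point they supply only the ceiling N = 66 per treatment and the roughly 66 − 56 = 10 planned withdrawals.

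**2. One subject followed through the rules.**
- The subject is dosed in Period 1, completes washout, attends Visit 5 and is withdrawn there before dosing.
- SAP 4: the Period 1 dose satisfies the ITT condition, which is per subject and not per period. The SAP's presumption that randomised subjects were dosed concerns ITT membership, so it does not help here.
- SAP 10.5.1: one Period 2 visit was attended, so the subject adds 1 to the N of the Period 2 treatment.
- SAP 10.4.1.2: with no first dose date in Period 2, no dated event can be on-treatment for that treatment. Later events go to the Period 1 treatment.
- SAP 10.6.2: exposure is derived from treatment start and stop dates by inhaler and period, so the subject has no Period 2 exposure.

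Protocol 5.6.1 names Visit 4 for the pregnancy test that Table 3 places at Visit 5. Those passages need reconciling, but this point does not depend on it: worsening first found at Visit 5, or consent withdrawn there, leads to the same result.

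**3. Direction.** The first Period 2 dose is given at Visit 5, so everyone dosed in Period 2 attended a Period 2 visit. The rule therefore cannot omit a dosed subject; it can only add undosed ones. In Period 1 the ITT dose condition already removes subjects known not to have been dosed, so the gap is specific to Period 2.

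**4. Size.** Let k be the number of subjects counted in a treatment's N but not dosed in that period. The documents give no k, so a range is shown. For e subjects with an event, the rule gives e/N and the dosed denominator gives e/(N − k). The relative understatement is 1 − (N − k)/N = k/N. With N = 66 and an illustrative e = 5:

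| k | Dosed N | Rule (5/66) | Dosed (5/(66 − k)) | Understatement k/66 |
|---|---|---|---|---|
| 0 | 66 | 7.58% | 7.58% | 0% |
| 1 | 65 | 7.58% | 7.69% | 1.5% |
| 2 | 64 | 7.58% | 7.81% | 3.0% |
| 3 | 63 | 7.58% | 7.94% | 4.5% |
| 5 | 61 | 7.58% | 8.20% | 7.6% |
| 10 | 56 | 7.58% | 8.93% | 15.2% |

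The last row is an implausible bound: every planned withdrawal at Visit 5, before dosing, and in the same sequence. Subjects who leave before Visit 5 reduce N below 66, so the effect per subject is slightly larger; at N = 56 it is 1/56 = 1.8%.

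**5. Display thresholds.** SAP Table 5 uses 3% cut-offs for common adverse events. With N between 56 and 66, two subjects give at least 2/66 = 3.03% and one gives at most 1/56 = 1.79%. Neither crosses the cut-off under either denominator.

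**The case against.** The strongest case against is that this may never happen.
- Subjects are told to contact the site if asthma worsens (Protocol 5.1).
- A severe exacerbation requires withdrawal whenever it occurs (Protocol 6.4.1).
- Withdrawal leads to an Early Withdrawal Visit, ideally within 24 hours (Protocol 6.4.4), which Table 3 lists apart from the scheduled Period 2 visits.

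Most subjects who deteriorate in washout would therefore leave before Visit 5 and never enter the Period 2 N. A k of 0 or 1 is quite possible. This stands, and it limits the size.

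It also disposes of a stronger reading: that subjects who worsen in washout after FF/VI would systematically enlarge the FP denominator and so bias the safety comparison against FF/VI. The usual exit for such subjects comes before Visit 5, and nothing in the documents indicates that Visit 5 withdrawals would fall mainly in one sequence.

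Three further points stand in part.
- The SAP does not state that adverse event percentages are divided by Big N, and the table shells are separate documents. However, SAP 10.5.3 defines N as the treatment group count, and no other safety denominator is named.
- An undosed subject could be traced through the planned attendance, exposure and actual-treatment displays. That makes the discrepancy detectable but does not correct the percentages.
- No safety hypothesis is tested, and the testing hierarchy in SAP 10.10.1 contains efficacy endpoints only.

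**Conclusion.** The point holds as a small defect in a counting convention. As written, SAP 10.5.1 puts an ITT subject withdrawn at Visit 5 before dosing into the safety denominator of a treatment not received. The direction is certain: N can only be too large and the percentages too low. The size is about 1.5% relative per such subject, assuming N = 66 and that percentages use Big N. It is zero if there are no such subjects.

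A reader might infer that efficacy is also affected. It is not: the primary endpoint and the tested secondary endpoints need FEV₁ from the end-of-period challenges, which such a subject does not have for Period 2.

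**What to change.** Add one sentence to SAP 10.5.1. For safety and exposure displays, each treatment's N is the number of ITT subjects who took at least one dose of double-blind medication in that period, with dosing presumed unless there is definitive evidence to the contrary. The presumption keeps attendees with missing dose dates from being dropped.

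Keep the attendance rule for disposition displays such as Tables 1.5 and 1.6, and keep randomised allocation for efficacy. Replacing N in every display would remove these subjects from the disposition tables and move efficacy off its stated basis.

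No new data are needed, because SAP 10.6.2 already uses treatment dates by period and inhaler. The cost is that N may differ slightly between safety and disposition tables, which a footnote can explain.
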